## PROTOCOL SYNOPSIS

Title	COVID-19 Vaccination Status and The Characteristics and Clinical Outcomes of Long COVID-19 Patients in [name] General Hospital
Sponsor	University of Indonesia
Study Rationale	
Long COVID is the persistence or emergence of symptoms for more than four weeks beyond the acute phase of Severe Acute Respiratory Syndrome – Coronavirus-2 (SARS-CoV-2) infection. Various multi-organ complications after COVID-19 infection include respiratory, cardiovascular, gastrointestinal, hepatobiliary, metabolic, and neuropsychiatric disorders. The symptoms and characteristics of Long COVID vary in each country.
 
Vaccination against SARS-CoV-2 has been documented to increase the clinical resolution of Long COVID. However, in Indonesia, current full-dose vaccination coverage has merely reached 15.6% of the national vaccination target. This condition can be predictably associated with a longer duration and higher severity of symptoms in Long COVID patients.
 
This study's point of view is to describe the incidence and the characteristic of long COVID in patients and the impact of COVID-19 vaccination on the clinical outcome of long COVID. In addition, this study is expected to reinforce the recommendation for the COVID-19 vaccine implementation in Indonesia. The result of this study can be applied in clinical practice to ascertain the benefits of SARS-CoV-2 vaccination to improve clinical outcomes and quality of life; and reduce symptoms, duration, and frequency of long COVID.

Study Objectives	
Primary
 
 
• To provide an overview of the symptoms and characteristics of Long COVID patients at [name] General Hospital.
 
• To determine whether vaccination against SARS-CoV-2 could improve clinical outcomes and quality of life of Long COVID patients at [name] General Hospital.
 
 
Secondary
 
 
• To determine whether vaccination against SARS-CoV-2 could increase functional exercise capacity of Long COVID patients.
 
• To determine whether vaccination against SARS-CoV-2 could reduce symptoms, duration, and frequency of Long COVID.
 

Study Design	Prospective cohort study

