Subject Population Key criteria for Inclusion and Exclusion:	
Inclusion Criteria
 
 
1. Adult patients, aged <math>\geq 18</math> years old with a history of laboratory-confirmed SARS-CoV-2 infection via a positive molecular (RT-PCR) or antigen (lateral flow assay) test, receiving outpatient/inpatient care from [name] General Hospital, any time prior to enrollment in this study.
 
2. Patients with/without comorbidities.
 
3. Willing to fill-out online Long COVID symptoms follow-up questionnaire.
 
4. Willing and able to comply with the trial protocol, 6 Minutes Walking Test (re-visits and physical testing).
 
 
Exclusion Criteria
 
 
1. Patients with no registered medical record number (MRN) at [name] General Hospital.
 
2. Refusal to participate in the study or to sign the informed consent form.
 
3. Contraindicated to perform the 6 Minutes Walking Test.
 
4. Patients with no access to a smartphone or computer (desktop, laptop, or tablet) to fill out the online screening questionnaire.
 
5. Patients who died during or before enrollment in the study.
 

Number of Subjects	
A total of 250 subjects are divided into 4 groups according to SARS-CoV-2 vaccination status:
 
 
• Never been vaccinated.
 
• Received 1st dose of vaccination.
 
• Received 2nd dose of vaccination.
 
• Received 3rd dose of vaccination.
 

Study Location	[name] General Hospital, Central Jakarta, Jakarta, Indonesia
Study Duration	Each subject's participation will last for 6 months. The estimated duration for the main protocol is approximately 1 year.
Study Phases	
Screening Screening for eligibility and obtaining consent.
 
Study Examination Online questionnaire filling, 6-Minute Walking Test (6MWT)
 
Follow-up Follow-up examination 3 and 6 months after baseline.

Safety Evaluations	
Adverse events will be monitored and collected by the study team from the point of signed consent until the adverse event(s) are resolved and subjects are stabilized. Adverse events will be managed according to the 6MWT guidelines of the American Thoracic Society (ATS).

---

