#### 5. Methods

##### 5.1. Study Design

This is a prospective cohort, cross-sectional study involving two hundred and fifty (250) subjects of post-acute COVID-19 patients, receiving outpatient/inpatient care from [name] General Hospital during the acute phase of the infection, any time prior to enrollment in this study.

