## 5.4. Data Collection

Data on age, sex, height, weight, body mass index, income, education, comorbidities, smoking, alcohol consumption, documented SARS-CoV-2 vaccination

status (including the amount, type, and when the vaccine was received), detailed history of laboratory-confirmed SARS-CoV-2 infection, Long COVID symptoms, severity, and duration are collected through online screening questionnaire.

Data on quality of life (QoL) are collected through St George's Respiratory Questionnaire (SGRQ) and Short Form (SF)-36 Health Survey self-assessment questionnaire at baseline, 3 and 6 months after enrollment. SGRQ addresses QoL in the domains of symptoms, activity, and impacts within the last 4 weeks; and the SF-36 Health Survey questionnaire addresses QoL in the domains of vitality, physical functioning, bodily pain, general health perceptions, physical and emotional and social role functioning.

Data on functional exercise capacity is measured using the Six-Minute Walking Test (6MWT) at baseline, 3 and 6 months after enrollment. The 6MWT is performed according to the guidelines of the American Thoracic Society (ATS). During the 6MWT, such data are collected: Blood pressure, oxygen saturation (SpO2), heart rate, dyspnea, and overall fatigue score using the Modified Borg scale before and after the test, and also one-time measurement (total distance walked in 6 minutes, symptoms at the end of exercise).

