## STATISTICAL ANALYSIS PLAN

### 1. Randomization

Subjects who meet all inclusion and exclusion criteria will be allocated into four groups; Never been vaccinated, received 1st dose, received 2nd dose, and received 3rd dose of vaccination. Subject allocation will be carried out through block randomization and known only by the pharmacist, and confidentiality is maintained so that subjects, doctors/nurses, researchers, and data analysers do not know the allocation of each subject.

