#### Analytic study: Prospective Cohort, consecutive sampling method

$$n = \left( \frac{Z_{\alpha}\sqrt{2PQ} + Z_{\beta}\sqrt{P1Q1 + P2Q2}}{P1 - P2} \right)^2 = \left( \frac{1.96\sqrt{2 \times 0.553 \times 0.447} + 0.80\sqrt{0.653 \times 0.347 + 0.453 \times 0.547}}{0.20} \right)^2$$

$$n = 93 \text{ subjects} \rightarrow N = 186 \text{ subjects}$$

Legends:

n : Number of subjects

$Z_{\alpha}$  : Z value in 95% confidence index = 1.96

$Z_{\beta}$  : Z value of test power = 0.80

$P_1 - P_2$  : Minimal difference in proportion considered significant = 0.20 ( $P_1 = 0.653$ )

Q : 1 - P

Assuming a 20% loss to follow-up event, the final sample size is:

$$n = 186 + (186 * 20\%)$$

$$n = 186 + 37$$

$$n = \mathbf{223 \text{ subjects}}$$

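### The SAP describes concealed, blinded block randomisation to vaccination groups, which this observational cohort cannot carry out

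*Combined protocol and SAP*

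**What the plan says.** SAP section 1 states that eligible subjects "will be allocated into four groups; Never been vaccinated" or one, two or three doses received. The mechanism is explicit: "Subject allocation will be carried out through block randomization and known only by the pharmacist". Confidentiality is kept "so that subjects, doctors/nurses, researchers, and data analysers do not know the allocation of each subject".

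The rest of the document describes a different study:

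- Synopsis, Study Design: "Prospective cohort study".
- Synopsis, Number of Subjects: "A total of 250 subjects are divided into 4 groups according to SARS-CoV-2 vaccination status".
- Protocol 5.1: "This is a prospective cohort, cross-sectional study involving two hundred and fifty (250) subjects".
- Protocol 5.4: the online screening questionnaire collects documented SARS-CoV-2 vaccination "status (including the amount, type, and when the vaccine was received".
- SAP section 2, in the same plan as the randomisation text: "Analytic study: Prospective Cohort, consecutive sampling method".

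The Synopsis lists the study phases as screening, then the questionnaire and six-minute walk test, then follow-up at 3 and 6 months. No vaccination visit or dispensing step is listed.

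**The concern.** The two accounts cannot both be followed, and the choice between them decides what the study can conclude. The objectives in Protocol 2.1 and 2.2 are causal: they ask whether vaccination improves outcomes, quality of life and exercise capacity. The planned comparison (Synopsis, Statistical and Analytic Plan; SAP 3.2.2) is an unadjusted chi-square or Fisher test. Randomisation is the one stated feature that would let an unadjusted test support a causal answer.

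Blinding matters for a second reason. The SGRQ, the SF-36 and the symptom data are self-reported by people who know whether they were vaccinated, so knowledge of exposure could influence the answers. The SAP claims a protection against this that is absent. A report that took its methods from SAP section 1 would describe a blinded randomised comparison that did not take place.

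**Working it through.** No arithmetic applies: the point rests on no figure in the plan, and the sample size calculation does not bear on it. The check sets the two accounts side by side.

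| Question | SAP section 1 | Rest of the document |
|---|---|---|
| What decides the group? | Block randomisation | Vaccination status (Synopsis, Number of Subjects) |
| When is it decided? | Once eligibility is met | When past doses were received; number, type and date are collected as history (Protocol 5.4) |
| Who knows it? | The pharmacist only | The subject, who fills out the questionnaire |
| Is a vaccine given by the study? | Suggested by the pharmacist's role | None described in the Study Phases or Protocol section 5 |
| Design label | Randomised, blinded | Prospective cohort (Synopsis; Protocol 5.1; SAP section 2) |

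1. **Randomisation.** Allocation by chance requires that exposure is still open when the subject is allocated. Here the dose history is collected as something that has already happened. A block list cannot change it.
2. **Concealment.** There is no future assignment to conceal. The pharmacist appears only in SAP section 1 and has nothing to hold or dispense.
3. **Subject blinding.** Subjects report their own doses, so they know their group.
4. **Staff and analyst blinding.** This could be arranged in part. Protocol 5.4 collects vaccination status and Long COVID symptoms in the same screening questionnaire, so anyone handling the raw data sees both. The text gives no procedure for separating them.
5. **Effect on the analysis.** Without randomisation, the groups may differ in anything related to getting vaccinated. Protocol 5.4 collects age, sex, income, education, comorbidities, smoking and infection history, but the text plans no adjustment for any of them.
6. **A rule is missing.** Because section 1 names randomisation as the mechanism, the SAP never says how, or as of what date, a subject is classified. Follow-up lasts 6 months, and the Introduction puts full-dose coverage at 15.6% of the national target. Further doses during follow-up are therefore plausible, and nothing says how they would be handled.

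The document labels agree only weakly with each other: Protocol 5.1 adds a cross-sectional label to the cohort one. None of them describes an allocated intervention.

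**The case against.** The strongest case on the other side is that this is leftover trial text that nobody could act on. The Synopsis states the true design, the allocation step cannot be performed, and deleting it would change no data point, test or sample size. SAP 3.2.2 justifies chi-square and Fisher by the nominal scale of the variables, not by randomisation. On this view the real threat is confounding under unadjusted tests, a separate defect that would remain after the deletion.

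Much of this is fair. Deleting the section does not repair the comparisons, and that a report would repeat the claim is a risk rather than a certainty. But the SAP is the document that defines the analysis, and section 1 is its only account of how the groups arise. A false statement there, beside causal objectives and unadjusted tests, is a substantive error.

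Three narrower points stand:

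- Masking the analyst, or the walk-test assessor, with coded labels is feasible. Strict impossibility applies to randomisation, allocation concealment and subject blinding.
- Consecutive sampling is compatible with randomisation, so the SAP section 2 heading contradicts section 1 through the word cohort. The Synopsis and Protocol 5.4 carry the argument.
- Trial wording also survives elsewhere: the inclusion criteria refer to a trial protocol, and Protocol section 9 to withdrawal from treatment. Neither describes an allocation.

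The figure under SAP 3.2 and the flow diagram were not available for this check. Neither could make a past vaccination history open to randomisation.

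**Conclusion.** The concern holds, and the text must be corrected. The randomisation, concealment and subject blinding in SAP section 1 cannot be carried out in the study described everywhere else. The error covers all four groups, all 250 planned subjects and every between-group comparison. The size of any resulting bias cannot be calculated, because the documents give no data on how vaccinated and unvaccinated patients differ.

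The conclusion assumes that the study gives no vaccine, which is what the available text shows. Correcting the wording makes the plan truthful; on its own it does not make the comparisons free of confounding.

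**What to change.** Replace SAP section 1 with a section titled Exposure classification that states:

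- Groups are assigned from documented vaccination records (number and dates of doses), not by allocation.
- Classification is made at a fixed reference date. The section says whether doses before and after the infection count alike, and how doses received during follow-up are handled.
- Subjects are not blinded to their vaccination status.
- Comparisons are observational and need adjustment for confounders, with the covariates and model named in SAP section 3. Conclusions are worded as associations.

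As an optional safeguard, give the analyst a dataset with coded group labels until the analysis code is final. Call this masked analysis only if it is done. Someone outside the analysis must hold the key, and unequal group sizes may give the labels away. Remove the remaining trial and treatment wording in the inclusion criteria and Protocol section 9 in the same amendment.

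**Cost.** The section 1 change is wording only. The adjusted analysis is modest extra work: candidate covariates are already collected under Protocol 5.4, but a model, missing-data handling and a check for sparse groups have to be specified. The study also gives up the description randomised or blinded, which it never met.

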## 5.3. Recruitment Methods

All patients, aged  $\geq 18$  years old with a history of laboratory-confirmed SARS-CoV-2 infection via a positive molecular (RT-PCR) or antigen (lateral flow assay) test, receiving outpatient/inpatient care from [name] General Hospital (any time prior to enrolment in this study) are offered to be a participant in this study. One of the research team, dr. [name] will be examining the supervision of the primary investigator, dr. [name], DIC, Ph.D., SpPD, and study coordinator, dr. [name], SpPD.

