## **5.5. Expected Outcomes**

It is the investigator's expectation that vaccination against SARS-CoV-2 could improve clinical outcomes and quality of life; and reduce symptoms, duration, and frequency of Long COVID.

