## **7. Consent Process**

Approval for medical treatment is obtained by first briefly explaining the background, objectives, and benefits of the research. The informed consent must be fully explained by the investigator or member of the study staff including the study aims, methods, benefits, and risks, and signed by the subject before enrollment into the study. Potential subjects will be informed that study participation is voluntary and that they may withdraw at any time. The subjects will be told that choosing against participation will not affect the care received for treatment. The subjects will be informed that they will be authorized access by investigational staff to confidential medical records. The subjects will be given sufficient time to read the consent and ask any questions. Research participants who are willing to take part in this study then sign an informed consent. Patients who are willing to participate in the study will receive compensation.

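### The masking claimed in SAP section 1 cannot operate for a vaccination history that subjects know and report, and no other rule keeps it from whoever runs the 6MWT

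*Combined protocol and SAP*

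**What the plan says.** SAP section 1 gives the mechanism, "Subject allocation will be carried out through block randomization and known only by the pharmacist", and the result claimed for it: "subjects, doctors/nurses, researchers, and data analysers do not know the allocation of each subject".

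The rest of the document describes a different kind of study. The synopsis says that 250 "subjects are divided into 4 groups according to SARS-CoV-2 vaccination status": none, one, two or three doses. Protocol 5.1 reads "This is a prospective cohort, cross-sectional study", and no section has the study giving a vaccine. Under protocol 5.4, subjects enter the number, type and dates of their doses in the online screening questionnaire.

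Protocol 5.4 also sets out the 6MWT at baseline, 3 and 6 months. It records vital signs and Borg dyspnoea and fatigue scores before and after the walk, plus "total distance walked in 6 minutes, symptoms at the end of exercise". The test is to follow the ATS guideline. The section does not say who runs it or what that person may know about the subject.

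**The concern.** Taken at face value, SAP section 1 tells a reader that outcome assessment and analysis were blinded. If the stated mechanism cannot deliver that and nothing else does, two things follow.

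First, the report would claim a protection the study did not have.

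Second, the walk is exposed to differential measurement. Distance depends on the subject's effort and on how the test is conducted, and exertion scores are subjective. An assessor who knows the subject's vaccination status can influence both without intending to. Protocol 5.5 records the investigator's "expectation that vaccination against SARS-CoV-2 could improve clinical outcomes and quality of life", so the direction of any lean would not be neutral. Adjusting for age or comorbidity does not remove an error introduced while the walk is being done. It has to be prevented at data collection.

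This is separate from the point that past vaccination cannot be randomised. Deleting the randomisation paragraph would correct the design description but leave outcome assessment with no masking provision at all.

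**Working it through.** The plan gives no figure on this point, so the check is mainly a comparison of sections.

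**Can the stated masking operate?**
- A pharmacist-held code hides an assignment that the study makes. Here the group is the subject's dose count before the study (synopsis, Number of Subjects), so there is no assignment to hide.
- Subjects know their own status. They cannot be masked to it.
- Subjects report that status to the study (protocol 5.4).
- Protocol section 11 limits access to patient files to the listed research team. It makes no division within the team. Section 7 has subjects authorise investigational staff to see their medical records, and the section 4 timeline places medical-record collection before the 6MWT phase.

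So the stated mechanism masks nobody.

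**Is there another rule that would mask the walk assessor?**
- Protocol 5.4: ATS guideline cited; nothing on withholding vaccination data.
- Protocol section 6: refers to the training of the person administering the test; nothing on masking.
- SAP section 3: nothing on coded groups for the analyst.

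None is stated.

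**Who runs the walk?** Protocol 5.3, under recruitment, says that one of the research team "will be examining the supervision of the primary investigator"; the sentence is garbled and does not mention the walk. The synopsis describes the study examination as the online questionnaire plus the 6MWT. Read together, these suggest a research-team member, but that is an inference. The gap does not depend on it, because no staff member is barred from the vaccination data.

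**Illustration of what a lean could do.** The documents give no size for assessor influence, so the lean d (in SD of walking distance) is assumed. With no true difference, n per group and a two-sided 0.05 test of two means:

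false-positive rate = P(|Z + d·√(n/2)| > 1.96)

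| n per group | Origin of n | d = 0.1 | d = 0.2 |
|---|---|---|---|
| 50 | 250 × 0.80 ÷ 4: equal groups after the SAP's 20% loss | shift 0.50, 7.9% | shift 1.00, 17.0% |
| 93 | per-group figure in SAP section 2 | shift 0.68, 10.5% | shift 1.36, 27.6% |
| 125 | 250 ÷ 2 | shift 0.79, 12.4% | shift 1.58, 35.3% |

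For example, with n = 93 and d = 0.1, √46.5 = 6.82, so the shift is 0.68 and the rate is 10.5%. The equal splits are also assumptions, because the documents fix no group sizes. SAP 3.2.2 names chi-square or Fisher's test rather than a comparison of means, so the table does not describe the planned analysis.

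**The case against.** The strongest case on the other side is that the test is standardised and the reach is narrow. Protocol 5.4 cites the ATS guideline. Protocol section 6 lists the reasons for ending a walk, calls participation self-directed, and puts premature termination for symptoms at 1% of tests. The 6MWT serves a secondary objective (protocol 2.2), while quality of life, in a primary objective, comes from self-assessment questionnaires that the walk assessor does not complete. All of that stands. It makes early stopping a weak route for bias and limits the point mainly to distance and Borg scores. It does not supply masking, because a standardised assessor can still know the group.

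Some stronger readings are tempting but not supported:
- *That the documents place a research-team member at the walk.* They suggest it; they do not say it.
- *That the team predicted better walking in vaccinated subjects.* Protocol 5.5 says vaccination could improve clinical outcomes and quality of life. It does not name exercise capacity.
- *That the walk results will be biased, or by a known amount.* The documents show an open route and nothing about its size. The percentages above follow from an assumed lean.
- *That consent makes matters worse.* Under protocol section 7, approval starts by "first briefly explaining the background, objectives, and benefits of the research". That is ordinary disclosure, and subjects could not be masked in any case.
- *That an encouragement script is missing, or that moving the vaccination items later in the questionnaire would help.* Whether the cited guideline supplies a script cannot be judged from these documents. Reordering would do little at 3 and 6 months, when status has already been reported.

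**Conclusion.** The point holds as a defect in the text and a gap in the plan. The masking statement in SAP section 1 cannot be true for this design, and no other provision keeps vaccination status from the walk assessor or the analyst. That conclusion rests on the documents alone.

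The consequence is possible differential measurement of walking distance and Borg scores, of unknown size, affecting a secondary objective. It assumes that whoever runs the walk can learn the subject's status. Nothing in the documents prevents this, but nothing shows that it happens. The illustrative false-positive rates of about 8% to 35% show only that a modest lean would matter if it occurred. They are not an estimate for this study.

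The correction is worth making because the plan already intends staff and analysts to be masked and lacks a means of achieving it.

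**What to change.** 1. In SAP section 1, replace the masking sentence with a description of the masking actually used, and state that subjects are not masked.
2. In protocol 5.4, state which existing staff role runs and records the 6MWT. State that this person has no access to a subject's vaccination answers or records until that subject's last walk is entered, and asks subjects not to mention vaccination.
3. In the SAP, state that the analyst works with coded group labels until the analysis is fixed.

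Cost: wording changes and an access restriction on data already collected online. Existing tasks may need to be divided so that the walk assessor does not also collect vaccination history or extract it from records. Masking will be partial, since some subjects will disclose their status.
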